8.7. Hospitalization

Hospitalization is defined as any initial admission (even less than 24 hours) in a hospital or equivalent healthcare facility or any prolongation of an existing admission. Admission also includes transfer within the hospital to an acute/intensive care unit (eg, from the psychiatric wing to a medical floor, medical floor to a coronary care unit, neurological floor to a tuberculosis unit). An emergency room visit does not necessarily constitute a hospitalization; however, the event leading to the emergency room visit should be assessed for medical importance.

Hospitalization does not include the following:

- Rehabilitation facilities;
- Hospice facilities;
- Respite care (eg, caregiver relief);
- Skilled nursing facilities;
- Nursing homes;
- Same day surgeries (as outpatient/same day/ambulatory procedures).

Hospitalization or prolongation of hospitalization in the absence of a precipitating, clinical AE is not in itself an SAE. Examples include:

- Admission for treatment of a preexisting condition not associated with the development of a new AE or with a worsening of the preexisting condition (eg, for work-up of persistent pre-treatment laboratory abnormality);
- Social admission (eg, patient has no place to sleep);
- Administrative admission (eg, for yearly physical examination);

- Protocol-specified admission during a study (eg, for a procedure required by the study protocol);
- Optional admission not associated with a precipitating clinical AE (eg, for elective cosmetic surgery);
- Hospitalization for observation without a medical AE;
- Pre-planned treatments or surgical procedures. These should be noted in the baseline documentation for the entire protocol and/or for the individual patient;
- Admission exclusively for the administration of blood products.

Diagnostic and therapeutic non-invasive and invasive procedures, such as surgery, should not be reported as AEs. However, the medical condition for which the procedure was performed should be reported if it meets the definition of an AE. For example, an acute appendicitis that begins during the AE reporting period should be reported as the AE, and the resulting appendectomy should be recorded as treatment of the AE.

8.8. Severity Assessment

If required on the AE CRFs, the investigator will use the following definitions of severity in accordance with CTCAE Version 4.0 (Publish Date: May 28, 2009, <http://ctep.cancer.gov/reporting/ctc.html>) to describe the maximum intensity of the AE. If the event is serious, the CTCAE grade reported in the AE CRF must be consistent with the description of CTCAE grade included in the narrative section of the SAE report.

GRADE	Clinical Description of Severity
0	No Change from Normal or Reference Range (This grade is not included in the Version 4.0 CTCAE document but may be used in certain circumstances.)
1	MILD Adverse Event
2	MODERATE Adverse Event
3	SEVERE Adverse Event
4	LIFE-THREATENING consequences; urgent intervention indicated
5	DEATH RELATED TO Adverse Event

Note the distinction between the severity and the seriousness of an AE. A severe event is not necessarily an SAE. For example headache may be severe (interferes significantly with patient's usual function) but would not be classified as serious unless it met one of the criteria for SAEs listed above.

8.9. Causality Assessment

The investigator's assessment of causality must be provided for all AEs (serious and non-serious); the investigator must record the causal relationship in the CRF, as appropriate, and report such an assessment in accordance with the serious adverse reporting requirements if applicable. An investigator's causality assessment is the determination of whether there exists a reasonable possibility that the investigational product caused or contributed to an AE; generally the facts (evidence) or arguments to suggest a causal relationship should be provided. If the investigator does not know whether or not the investigational product caused the event, then the event will be handled as "related to investigational product" for reporting purposes, as defined by the Sponsor (refer to the Section on [Reporting Requirements](#)). If the investigator's causality assessment is "unknown but not related to investigational product", this should be clearly documented on study records.

In addition, if the investigator determines that an SAE is associated with study procedures, the investigator must record this causal relationship in the source documents and CRF, as appropriate, and report such an assessment in accordance with the SAE reporting requirements, if applicable.

8.10. Exposure During Pregnancy

For both unapproved/unlicensed products and for marketed products, an exposure during pregnancy occurs if:

- A female becomes, or is found to be, pregnant either while receiving or having been exposed (eg, because of treatment or environmental exposure) to the investigational product; or the female becomes, or is found to be pregnant after discontinuing and/or being exposed to the investigational product;
- An example of environmental exposure would be a case involving direct contact with a Pfizer product in a pregnant women (eg, a nurse reports that she is pregnant and has been exposed to chemotherapeutic products).
- A male has been exposed (eg, because of treatment or environmental exposure) to the investigational product prior to or around the time of conception and/or is exposed during his partner's pregnancy.

If a study patient or study patient's partner becomes or is found to be pregnant during the study patient's treatment with the investigational product, the investigator must submit this information to the Pfizer drug safety unit on a Serious Adverse Event (SAE) Report Form and Exposure During Pregnancy (EDP) supplemental form, regardless of whether an SAE has occurred. In addition, the investigator must submit information regarding environmental exposure to a Pfizer product in a pregnant woman (eg, a patient reports that she is pregnant and has been exposed to a cytotoxic product by inhalation or spillage) using the EDP supplemental form. This must be done irrespective of whether an AE has occurred and within 24 hours of awareness of the exposure. The information submitted should include the

anticipated date of delivery (see the below for information related to termination of pregnancy).

Follow-up is conducted to obtain general information on the pregnancy and its outcome for all EDP reports with an unknown outcome. The investigator will follow the pregnancy until completion (or until pregnancy termination) and notify Pfizer of the outcome as a follow up to the initial EDP supplemental form. In the case of a live birth, the structural integrity of the neonate can be assessed at the time of birth. In the event of a termination, the reason(s) for the termination should be specified and, if clinically possible, the structural integrity of the terminated fetus should be assessed by gross visual inspection (unless pre-procedure test findings are conclusive for a congenital anomaly and the findings are reported).

If the outcome of the pregnancy meets the criteria for an SAE (ie, ectopic pregnancy, spontaneous abortion, intrauterine fetal demise, neonatal death, or congenital anomaly [in a live born, a terminated fetus, an intrauterine fetal demise or a neonatal death]), the investigator should follow the procedures for reporting SAEs.

Additional information about pregnancy outcomes that are reported as SAEs follows:

- Spontaneous abortion includes miscarriage and missed abortion;
- Neonatal deaths that occur within 1 month of birth should be reported, without regard to causality, as SAEs. In addition, infant deaths after 1 month should be reported as SAEs when the investigator assesses the infant death as related or possibly related to exposure to the investigational product.

Additional information regarding the exposure during pregnancy may be requested by the investigator. Further follow-up of birth outcomes will be handled on a case-by-case basis (eg, follow-up on preterm infants to identify developmental delays). In the case of paternal exposure, the investigator will provide the study patient with the Pregnant Partner Release of Information Form to deliver to his partner. The Investigator must document in the source documents that the patient was given the Pregnant Partner Release of Information Form to provide to his partner.

8.11. Occupational Exposure

An occupational exposure occurs when during the performance of job duties, a person (whether a healthcare professional or otherwise) gets in unplanned direct contact with the product, which may or may not lead to the occurrence of an adverse event.

An occupational exposure is reported to the drug safety unit within 24 hours of Investigator's awareness, using the SAE Report form, regardless of whether there is an associated AE/SAE. Since the information does not pertain to a patient enrolled in the study, the information is not reported on a CRF, however a copy of the completed SAE Report form is maintained in the investigator site file.

8.12. Withdrawal Due to Adverse Events (Refer to the Section [Patient Withdrawal](#))

Withdrawal due to AEs should be distinguished from withdrawal due to other causes, according to the definition of AE noted earlier, and recorded on the appropriate AE CRF page.

When a patient withdraws because of a SAE, the SAE must be reported in accordance with the reporting requirements defined below.

8.13. Eliciting Adverse Event Information

The investigator is to report all directly observed AEs and all AEs spontaneously reported by the study patient. In addition, each study patient will be questioned about AEs.

8.14. Reporting Requirements

Each AE is to be assessed to determine if it meets the criteria for SAEs. If an SAE occurs, expedited reporting will follow local and international regulations, as appropriate.

8.14.1. Serious Adverse Event Reporting Requirements

If an SAE occurs, Pfizer is to be notified within 24 hours of investigator awareness of the event. In particular, if the SAE is fatal or life-threatening, notification to Pfizer must be made immediately, irrespective of the extent of available AE information. This timeframe also applies to additional new information (follow-up) on previously forwarded SAE reports as well as to the initial and follow-up reporting of exposure during pregnancy, exposure via breastfeeding, and occupational exposure cases.

In the rare event that the investigator does not become aware of the occurrence of an SAE immediately (eg, if an outpatient study patient initially seeks treatment elsewhere), the investigator is to report the event within 24 hours after learning of it and document the time of his/her first awareness of the AE.

For all SAEs, the investigator is obligated to pursue and provide information to Pfizer in accordance with the timeframes for reporting specified above. In addition, an investigator may be requested by Pfizer to obtain specific additional follow-up information in an expedited fashion. This information collected for SAEs is more detailed than that captured on the AE CRF. In general, this will include a description of the AE in sufficient detail to allow for a complete medical assessment of the case and independent determination of possible causality. Information on other possible causes of the event, such as concomitant medications, vaccines, and/or illnesses must be provided. In the case of a patient death, a summary of available autopsy findings must be submitted as soon as possible to Pfizer or its designated representative.

8.14.2. Non-Serious Adverse Event Reporting Requirements

All AEs will be reported on the AE page(s) of the CRF. It should be noted that the form for collection of SAE information is not the same as the AE CRF. Where the same data are collected, the forms must be completed in a consistent manner. For example, the same AE

term should be used on both forms. AEs should be reported using concise medical terminology on the CRFs as well as on the form for collection of SAE information.

8.14.3. Sponsor's Reporting Requirements to Regulatory Authorities

Adverse event reporting, including suspected unexpected serious adverse reactions, will be carried out in accordance with applicable local regulations.

9. DATA ANALYSIS/STATISTICAL METHODS

Detailed methodology for summary and statistical analyses of the data collected in this trial will be documented in a Statistical Analysis Plan (SAP), which will be maintained by Pfizer. The SAP may modify the plans outlined in the protocol; however, any major modifications of the primary endpoint definition and/or its analysis will also be reflected in a protocol amendment. Unless otherwise stated, the monotherapy cohort and the combination cohorts will be analyzed separately. The data from the Continuation Cohort will not be analyzed and will be presented in the form of patient data listings separately from the other cohorts.

The primary analysis will be performed after disease assessment on Cycle 9/Day 1 for the last (15th) patient treated in Expansion Cohort of LDAC combination for efficacy. The timing of the primary analysis is estimated to be after approximately 19 months after the first dose for the first patient in Expansion Cohort of LDAC combination for efficacy, assuming the enroll speed as 15 patients per year.

The final analysis will be performed after all patients have died or after the last patient last visit, whichever occurs first. Further analyses could be performed, if necessary.

9.1. Analysis Sets

In this study, analysis sets are defined as below although the patients enrolled in the Expansion Cohort of LDAC combination for efficacy are excluded from DLT-evaluable analysis set and the patient enrolled in the Continuation Cohort is excluded from all of these analysis sets except the safety analysis set. The patient enrolled in the Continuation Cohort is included in the safety analysis set if the patient receives at least one dose of study medication.

1. Safety analysis set:

The safety analysis set includes all enrolled patients who receive at least one dose of study medication.

2. Full analysis set:

The full analysis set includes all enrolled patients who receive at least one dose of study medication on or after Cycle 1/Day 1 (Induction Cycle/Day 1 for fit patients in the Combination Cohort 2).

3. DLT-evaluable analysis set:

The per protocol analysis set includes all enrolled patients who receive at least one dose of study medication and who do not have major treatment deviations during first cycle (DLT observation period). Patients with major treatment deviations during the DLT observation period are not evaluable for the DLT assessment and will be replaced as needed. Major deviations include, but are not limited to, administration of less than 80% of the planned dose during the DLT observation period of PF-04449913 or any component of the combination therapy [LDAC for Combination Cohort 1 (Unfit Patients), cytarabine/daunorubicin for Combination Cohort 2 (Fit Patients), and azacitidine for Combination Cohort 3 (Azacitidine Combination)] for reasons other than drug related toxicity.

4. PK analysis sets:

The PK concentration population is defined as all treated patients who have at least 1 concentration of any of the study drugs. The PK parameter analysis population is defined as all treated patients who have at least one of the PK parameters of interest of any of the study drugs.

5. QTc-evaluable analysis set:

The QTc-evaluable dataset is defined as all patients who have baseline and at least one triplicate ECG assessment after having at least one PF-04449913 dose on study.

9.2. Sample Size Determination

Cohorts excluding the Expansion Cohort of LDAC combination for efficacy

No statistical sample size determination was performed. The number of patients to be enrolled in the study depends on the observed safety profile within the cohorts. The total expected number of patients is estimated to be 34 patients.

The Expansion Cohort of LDAC combination for efficacy

The total expected number of patients is estimated to be 15 patients.

A one stage design with 15 patients provides 80.8% power with a one-sided type I error rate of 0.05 to test the null hypothesis that the true investigator-reported DMR rate is 6.8% vs the alternative hypothesis that the investigator-reported DMR rate is 34.1%. The study would be considered positive if 4 responses are observed. The null DMR rate and the alternative DMR rate are based on the result of the analysis based on the derived response for B1371003 CSR (P2 Unfit, data cut off: 3 Jan 2017).

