The primary analysis of OS was conducted after 92 OS events observed. As a result, statistically and clinically significant improvement of OS prolongation in LDAC + PF-04449913 arm was observed (mOS for LDAC + PF-04449913 was 8.3 months vs 4.9 months for LDAC alone; stratified HR of 0.537 [80% CI: 0.407, 0.708]; 1-sided stratified log-rank p-value 0.0017) (data cut off: 13 Apr 2016). This result was consistent with the updated analysis in the CSR (mOS 8.8 months vs 4.9 months; stratified HR=0.513 (80% CI: 0.394, 0.666; stratified p=0.0004) (data cut off, hereafter: 3 Jan 2017). CR and DMR^a rates based on derived response for PF-04449913 + LDAC were 17.0% (15/88) and 34.1% (30/88) versus 2.3% (1/44) and 6.8% (3/44) for LDAC alone, respectively. The safety profile of PF-04449913 100 mg combined with LDAC and LDAC alone was tolerable and manageable: The most commonly-reported AEs in the PF-04449913 100 mg+LDAC arm were cytopenia and gastrointestinal disorder. Cytopenias were not accompanied by higher rates of infections or bleeding as compared to the LDAC alone arm. SAEs of febrile neutropenia (28.6% versus 17.1%) and pneumonia (22.6% versus 17.1%) were more frequent in the PF-04449913 100 mg+LDAC arm than in the LDAC alone arm. In contrast, SAE of

^a Disease Modifying Response (DMR) rate includes Complete Remission (CR), CR with incomplete blood count recovery (CRi), Morphologic Leukemia-Free State (MLFS), marrow CR (mCR) and Partial Remission (PR) ([Appendix 5](#) and [Appendix 8](#)).

sepsis (3.6% versus 12.2%) was less frequently reported for the PF-04449913+LDAC arm versus the LDAC alone arm.

In P2 Fit arm (cytarabine/daunorubicin + PF-04449913), the primary analyses were planned for patients age ≥ 55 years old. For the primary endpoint, 22 (36.7%) patients achieved CR based on derived response for patients ≥ 55 years old. For OS of the secondary endpoint, the estimated mOS was 14.7 months for patients ≥ 55 years old. The safety profile of PF-04449913 100 mg combined with cytarabine/daunorubicin for patients in the P2 Fit arm was tolerable and manageable. The most frequently reported AEs ($\geq 50\%$) in the P2 Fit arm were diarrhoea, febrile neutropenia, nausea and hypokalaemia.

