4. HYPOTHESES AND DECISION RULES

4.1. Statistical Hypotheses

For the Expansion Cohort of LDAC combination for efficacy (Unfit Patients), a total of 15 patients will provide 80.8% power to reject the null hypothesis DMR rate=6.8% when the true DMR rate=34.1% for the alternative hypothesis. The DMR rates for the hypotheses are based on the result of the analysis based on the derived response for B1371003 CSR (P2 Unfit, data cut off: 3 Jan 2017).

For other cohorts, there are no formal statistical hypotheses. The emphasis of the primary analysis will be on estimation of key summary statistics.

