The combination of PF-04449913 and LDAC will be considered superior to the historical data of LDAC as single-agent with respect to DMR if the DMR rate is statistically significant at the 1-sided 0.05 level using exact test for a single proportion. An observed DMR rate of 26.7% or above (eg, 4 or more responders out of 15 patients) will reject the null hypothesis.

Combination Cohort 2 (Fit Patients):

A total of 6 patients will be treated in this cohort and followed up for DLT evaluation. If ≤ 1 of the 6 patients experiences a DLT event by the end of Induction Cycle 1, the tolerability of the combination will be confirmed. If more than 2 of the 6 patients experience a DLT by the end of Induction Cycle 1, additional lower dose levels may be tested using identical criteria to those outlined above with respect to DLT events.

Combination Cohort 3 (Azacitidine Combination):

A total of 6 patients will be treated in this cohort and followed up for DLT evaluation. The DLT evaluation period includes the first cycle of treatment. If ≤ 1 of the 6 patients experiences a DLT by the end of Cycle 1, the tolerability of the combination will be deemed confirmed. If more than 2 of the 6 patients experience a DLT by the end of Cycle 1, the investigator and the sponsor will review all available safety data and discuss the next steps.

Continuation Cohort:

No decision rule for this cohort.

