6.1. Efficacy Endpoints (excluding the Continuation Cohort)

The efficacy endpoints of the disease response per investigator evaluation based on the Response Criteria CRF pages (see Protocol Appendix 5 through Appendix 9) is the primary method of documentation of disease. The response criteria differ for each hematologic malignancy (see [Appendix 2](#) through [Appendix 5](#) for details). Objective Response (OR) needs to be established before any subsequent documentation of progression.

The following dates are identified.

- The first objective response date: the assessment date of first documented objective response. However, these responses for MDS, CMML and CML need to be confirmed as described above.
- The first progression date: the assessment date of first documented (objective) disease progression.
- The first relapse date (except for CML): the assessment date of first documented relapse.
- The last disease assessment date: the date of last disease assessment date.

Combination Cohort 1 (Unfit Patients) and Expansion Cohort of LDAC combination for efficacy (Unfit Patients):

The following efficacy endpoints are defined.

DMR and its rate includes complete remission (CR), CR with incomplete blood count recovery (CRi), morphologic leukemia-free state (MLFS), marrow CR (mCR) and partial remission (PR) (see Protocol Appendix 5 and Appendix 8).

OS is defined as the time from the date of first dose of study drug to the date of death due to any cause. Patients last known to be alive will be censored at the date of last contact. The primary interest is the survival probability at 6 months and at 12 months.

Duration of response is only defined for patients who have ever achieved CR/CRi on study as the time from the date of first documentation of a CR/CRi (Protocol Appendix 5 and Appendix 8) to the date of loss of response after CR/CRi or death due to any cause. Duration of response data will be censored on the date of the last adequate response assessment for patients who do not have an event (loss of response or death). Duration of DMR for patients who have ever achieved DMR on study is also defined.

Time to response is only defined for patients who have ever achieved CR/CRi on study as the time from the date of first dose of study drug to the date of first documentation of a CR/CRi. Time to DMR for patients who have ever achieved DMR on study is also defined.

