Appendix 2. Response Criteria for Myelodysplasia and CMML

Objective response and Disease Progression

The objective status at each evaluation is determined per investigator evaluation (Protocol Appendix 5). However, the status will be verified per clinical judgment by the Sponsor. More specifically, the following categories on the CRF page will be considered objective response and disease progression for the purpose of this study.

Objective Response (OR)

Disease status assessments (if available)

- Complete remission (CR);
- Partial remission (PR);
- Marrow complete remission (mCR).

Cytogenetic response (if available)

- Complete cytogenetic response;
- Partial cytogenetic response.

Hematologic improvement (if available)

- Erythroid response;
- Platelet response;
- Neutrophil response.

Objective Disease Progression

Disease status assessments (if available)

- Disease progression;
- Failure;
- Relapse after CR or PR.

Cytogenetic response (if available)

- Loss of cytogenetic response.

Hematologic improvement (if available)

- Progression or relapse after HI.

Relapse

Disease status assessments (if available)

- Relapse after CR or PR.

Cytogenetic response (if available)

- Loss of cytogenetic response.

Hematologic improvement (if available)

- Progression or relapse after HI.

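### The Expansion Cohort is scored by investigator-reported DMR but tested against derived-response rates from B1371003, and no derived DMR rate is planned for the cohort

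*Protocol*

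**What the plan says.** Protocol 9.2 states both hypotheses for the investigator-reported rate: it tests "the null hypothesis that the true investigator-reported DMR rate is 6.8" per cent, against an alternative of 34.1%. The same paragraph says that the two rates "are based on the result of the analysis based on the derived response for B1371003 CSR", for the Phase 2 unfit population. SAP 4.1 repeats the source: "The DMR rates for the hypotheses are based on the result of the analysis based on the derived response for B1371003 CSR".

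Protocol 1.2.8.1.3 gives the counts. CR and DMR "rates based on derived response for PF-04449913 + LDAC were 17.0% (15/88) and 34.1% (30/88") respectively, and LDAC alone had a DMR of 3/44 (6.8%).

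For the present study, SAP 6.1 takes "disease response per investigator evaluation based on the Response Criteria CRF pages" as the primary way of documenting response. SAP Appendix 2 (MDS) adds: "However, the status will be verified per clinical judgment by the Sponsor". Appendix 4 (AML) says the same.

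SAP 8.2.1 plans one DMR test on the Full Analysis Set, with a p-value and 90% and 95% confidence intervals. SAP 8.2.2.1 summarises the same DMR for AML, MDS and both together. SAP 8.2.3 uses DMR only to divide patients for the survival and transfusion subsets. Neither document describes a derivation algorithm for DMR or plans a derived DMR rate.

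**The concern.** A single-arm test against a historical rate depends on both sides being measured alike. Here the sponsor's own wording separates two ascertainments, investigator-reported and derived, and uses one for the cohort and the other for the benchmark.

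This is the only formal test in the study: "For other cohorts, there are no formal statistical hypotheses" (SAP 4.1). Under SAP 4.2 a significant result means that the combination "will be considered superior to the historical data of LDAC as single-agent with respect to DMR". With 15 patients and a threshold of 4, a single patient classified differently by derivation could decide that statement, and no planned summary would show whether this had happened.

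**Working it through.** **Inputs.** n = 15, one-sided alpha 0.05, exact test for a single proportion, success at 4 or more responders (Protocol 9.2, SAP 4.2). Null 6.8% and alternative 34.1% (Protocol 9.2), from 3/44 and 30/88 (Protocol 1.2.8.1.3).

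**Step 1: reproduce the plan.** Let X be binomial (15, p), so that P(X≥4) = 1 − Σ C(15,k) p^k (1−p)^(15−k), summed over k = 0 to 3.

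- At p = 0.341: P(X = 0, 1, 2, 3) = 0.0019, 0.0149, 0.0540, 0.1210. The power is 1 − 0.1918 = 0.808, which matches the stated 80.8%.
- At p = 0.068: P(X = 0, 1, 2, 3) = 0.3477, 0.3806, 0.1944, 0.0615. The attained type I error is 1 − 0.984 = 0.016.
- A threshold of 3 would give 0.016 + 0.0615 = 0.077, above 0.05. So 4 is the right boundary.

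**Step 2: effect of reclassifying a patient in the cohort.** One-sided exact p-values at the 6.8% null, with Clopper-Pearson 90% intervals:

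| Responders | p | 90% CI |
|---|---|---|
| 3/15 | 0.077 | 5.7% to 44.0% |
| 4/15 | 0.016 | 9.7% to 51.1% |
| 5/15 | 0.002 | 14.2% to 57.7% |

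If exactly 4 patients respond by investigator report, one not confirmed by derivation makes the result non-significant. At 5, it takes two. If exactly 3 respond by investigator report, one extra derived responder works the other way.

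At the design alternative, P(X=4) = 0.188, which is 0.188/0.808 = 23% of positive outcomes. P(X=3) is 0.121, so the count falls on one side or the other of the boundary with probability 0.188 + 0.121 = 0.31.

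**Step 3: effect on the benchmark (assumption).** The documents give no investigator-reported DMR rate for LDAC in B1371003. Suppose that it had differed from 3/44 by one or two patients. The type I error of the rule of at least 4 in 15 would then be:

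| Assumed LDAC rate | P(X≥4) |
|---|---|
| 2/44 | 0.004 |
| 3/44 (as planned) | 0.016 |
| 4/44 | 0.041 |
| 5/44 | 0.082 |

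The rule keeps the 5% level up to a null rate of 9.67%, the root of P(X≥4) = 0.05.

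For scale, the exact 95% interval of 3/44 is 1.4% to 18.7%, over which P(X≥4) runs from below 0.001 to 0.302. The assumed range in the table lies well inside that sampling uncertainty. It shows sensitivity and does not demonstrate an error.

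**The case against.** The case against giving this much weight is substantial, and several parts of it stand.

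- **The endpoint is the same.** The footnote in Protocol 1.2.8.1.3 defines the B1371003 DMR by the same five categories (CR, CRi, MLFS, mCR, PR) and the same Appendices 5 and 8 as here. A reader might infer that the two studies measure different endpoints. They do not; only the way in which the criteria are applied differs. The sponsor's verification is a partial check, although it has no stated algorithm and no output of its own.
- **Most of the raw material will be visible.** SAP listings cover disease response (8.2.2.1), transfusions (8.2.2.5), laboratory values (8.2.4.2), bone marrow (8.2.10.4), immunophenotyping and cytogenetics (8.2.10.5) and extramedullary disease (8.2.10.7). A patient-by-patient check is largely possible from these. What is missing is a derived rate and its comparison with the investigator's.
- **Type I error.** A reader might infer that the test is anti-conservative. The documents do not support this. The attained level is 0.016, and two more LDAC responders by investigator report than by derivation (5/44 rather than 3/44) would be needed to exceed 0.05. The difference could equally make the test more conservative.
- **Small samples.** A one-patient margin is a feature of any threshold design with 15 patients. That is true, but here the reclassification has a specific, named source that could be checked cheaply.
- **Amendment 8.** It ended required CRF reporting of blood counts and transfusions and the requirement for immunophenotyping in this cohort (Protocol Table 3 footnotes). A reader might infer that derivation is now impossible. Nothing shows that data needed for the primary analysis were affected.

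The source of the rates is also stated openly in both documents, so nothing is concealed.

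**Conclusion.** The point holds as an unlike-for-like ascertainment that the plan does not examine, in the one cohort with a formal test. It does not invalidate the design: the power, type I error and threshold are correct for the hypotheses as written.

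Its demonstrated size is one patient. At exactly 4 responders, a single patient not confirmed by derivation moves p from 0.016 to 0.077 and removes the superiority statement of SAP 4.2. How often investigator and derived response disagree, and in which direction, cannot be learned from the documents. The benchmark-side figures therefore rest on assumed LDAC counts. A supportive analysis is a cheap improvement rather than a condition for the test to stand.

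**What to change.** Leave the primary test, the 6.8% null and the threshold of 4 in 15 unchanged. The study is open-label, and the interim in SAP section 3 depends on the responder count. Protocol 1.2.8 reports 45 patients treated as of 29 January 2020; if no more than the expected 34 were in other cohorts, at least 45 − 34 = 11 of these 15 were already on treatment. Resetting the null now would do more harm than the mismatch.

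In SAP 8.2.1 add, as supportive:

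1. DMR by the B1371003 derived-response algorithm, cited or written out, with the same exact test and 90% and 95% intervals.
2. A cross-table of investigator against derived DMR for the 15 patients.
3. The number of patients whose response cannot be derived. SAP 7.2 would otherwise count them as non-responders without showing it.

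Report these beside the SAP 4.2 conclusion. If responses are already known when the analysis is written, label it as added during an open-label study.

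The cost is a SAP revision and some programming, the amount depending on an algorithm that neither document contains. No patients or procedures are added. The primary endpoint and its analysis do not change, so Protocol section 9 does not call for a protocol amendment. The downside is a second result that may be less favourable, or incomplete if some CRF data were not recorded after Amendment 8.
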